7.6.1.1.2 Complicated Urinary Tract Infection

- **Clinical Cure:** Resolution or substantial improvement of baseline signs and symptoms of cUTI, or return to preinfection baseline if known, such that no antibiotic therapy is required for the treatment of the current infection.
- **Clinical Failure:** No apparent response to therapy; persistence or worsening of baseline signs and/or symptoms of cUTI; or reappearance of signs and/or symptoms of cUTI; development of new signs and/or symptoms of cUTI requiring antibiotic therapy other than, or in addition to, study treatment therapy; or death due to cUTI.
- **Indeterminate:** Lost to follow-up such that a determination of clinical cure/failure cannot be made.

7.6.1.1.3 BSI/Sepsis

- **Clinical Cure:** Resolution or substantial improvement of baseline signs and symptoms. Subjects with bacteremia must have eradication of bacteremia caused by the Gram-negative pathogen.
- **Clinical Failure:** No apparent response to therapy; persistence or worsening of baseline signs and/or symptoms, reappearance of signs and/or symptoms; development of new signs and/or symptoms requiring antibiotic therapy other than, or in addition to, study treatment therapy; or death due to BSI/sepsis.
- **Indeterminate:** Lost to follow-up such that a determination of clinical cure/failure cannot be made.

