Blood samples for determination of plasma cefiderocol concentrations will be collected from each subject at prespecified time points during and/or after the cefiderocol infusion ([Section 7.4](#)). Cefiderocol PK will be determined in the single-dose phase in each of the cohorts; cefiderocol dose recommendations may be revised by the sponsor prior to initiating enrollment of subjects in the multiple-dose phase of each respective cohort.

In the multiple-dose phase only, clinical outcome data and microbiological outcome data will be obtained. Clinical and microbiological outcome assessments will be performed at EOT, at the Posttreatment visit (7 \pm 4 days after EOT), and EOS if available. Data from assessments performed prior to, during, and after treatment with SOC antibiotics as part of routine patient care will be captured as study data. The time points for collection of microbiological specimens are otherwise not prespecified by the protocol (Posttreatment Visit, EOT, and EOS, if available; [Section 7.6](#)). In subjects where it is not possible to obtain a posttreatment culture and/or EOS culture, determination of presumed microbiological eradication may be made based on resolution of all presenting clinical sign and symptoms of the infection (clinical cure).

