7.5.3.2 Microbiologic Cultures

Appropriate clinical specimens (eg, urine, blood, sputum, swabs) should be obtained if possible from all subjects prior to the start of any antibiotic treatments and also prior to starting study treatment. Clinical specimens for microbiologic cultures are to be sent to the local laboratory for identification of all pathogens causing the infection. Urine should be grown quantitatively with appropriate method-specific dilutions. Blood cultures should be collected if clinically indicated and sent to the local laboratory. After initiation of study treatment in the multiple-dose phase, clinical specimens should be obtained where possible, if clinically indicated. Culture results obtained prior to informed consent/assent, but directly related to the current infection, should be recorded and may form the basis for subject inclusion in the study.

Local culture results for subjects enrolled in the single-dose phase should be recorded in the subject medical records, and local culture results for subjects enrolled in the multiple-dose phase should be recorded in the eCRF. Identified isolates from subjects in the multiple-dose phase should be sent to the central laboratory.

If possible, all baseline microbiological specimens should also have a Gram stain performed. In addition, quantification results for cultures will be collected. The high-power microscopic view of the Gram stain can be used to characterize the general type of bacteria causing the infection (eg, a Gram-positive or a Gram-negative bacterial pathogen). A report of both inflammatory cells and bacteria is necessary. A Gram stain result showing the presence of Gram-negative bacteria is a primary indication of the infection that will be most appropriate for this study.

Inappropriate clinical specimens should not be used for confirmatory culture identification of causative pathogens.

All isolated pathogens will be frozen and stored for later shipping to the central laboratory. Detailed procedures for sample collection, handling, labeling, storage, and shipping will be provided in the separate study laboratory manual. Shipping labels, instructions for shipping, and courier service will be provided from the sponsor or CRO.

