7.6.2.1.1 HAP/VAP/cIAI and BSI/Sepsis

- **Eradication:** Absence of the baseline Gram-negative pathogen from an appropriate clinical specimen. If it is not possible to obtain an appropriate clinical culture and the subject has a successful clinical outcome, the response will be presumed to be eradication.
- **Persistence:** Continued presence of the baseline Gram-negative pathogen from an appropriate clinical specimen.
- **Indeterminate:** No culture obtained from an appropriate clinical specimen or additional antibiotic therapy for the treatment of the current infection including missed sampling.

7.6.2.1.2 cUTI

- **Eradication:** A urine culture shows the baseline Gram-negative uropathogen found at entry at $\geq 10^5$ colony forming units (CFU)/mL are reduced to $< 10^3$ CFU/mL.
- **Persistence:** A urine culture shows that the baseline Gram-negative uropathogen found at entry at $\geq 10^5$ CFU/mL grows $\geq 10^3$ CFU/mL.

- **Indeterminate:** No urine culture obtained or additional antibiotic therapy for the treatment of the current infection including missed sampling.

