- Microbiological outcome per pathogen defined as the categories below:

HAP/VAP/cIAI and BSI/Sepsis:

- Persistence: Continued presence of the baseline Gram-negative pathogen from an appropriate clinical specimen.
- Indeterminate: No culture obtained from an appropriate clinical specimen or additional antibiotic therapy for the treatment of the current infection including missed sampling for reasons other than a successful clinical outcome.
- Eradication: Absence of the baseline Gram-negative pathogen from an appropriate clinical specimen. If it is not possible to obtain an appropriate clinical culture and the subject has a successful clinical outcome, the response will be presumed to be eradication.

cUTI:

- Persistence: A urine culture shows that the baseline Gram-negative uropathogen found at entry at $\geq 10^5$ CFU/mL grows to $\geq 10^3$ CFU/mL.
- Indeterminate: No urine culture obtained or additional antibiotic therapy for the treatment of the current infection including missed sampling.
- Eradication: A urine culture shows that the baseline Gram-negative uropathogen found at entry at $\geq 10^5$ colony forming units (CFU)/mL is reduced to $< 10^3$ CFU/mL.

Clinical response will be characterized based on an evaluation of clinical signs and symptoms by the investigator or designee. Clinical outcomes will be characterized at EOT, Posttreatment, and EOS if available.

The microbiological outcomes per subject determined by investigator will be entered in the eCRF. When the investigator confirms:

- that the subject experiences eradication of all baseline Gram negative pathogens then “Eradication” will be entered. For subjects with baseline infection other than cUTI who achieved clinical cure at corresponding visit, the response will be considered as Eradicated.
- that the subject experiences persistence of any baseline Gram-negative pathogen then “Persistence” will be entered
- that the subject experiences anything other than above then “Indeterminate” will be entered.

Emergent (ie, nonbaseline) pathogens will be considered separately, and will not affect the per-subject microbiological outcome.

This document is confidential.

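### For a bacteraemic child with no follow-up blood culture, BSI/sepsis clinical cure and eradication each depend on the other, so the definitions settle neither

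*Protocol*

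**What the plan says.** **Clinical cure.** Protocol 7.6.1.1.3 defines cure in BSI/sepsis by resolved or substantially improved signs and symptoms, and adds: "Subjects with bacteremia must have eradication of bacteremia caused by the Gram-negative pathogen". It does not say that eradication must be shown by a culture. SAP section 8 repeats the sentence.

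**Eradication.** Protocol 7.6.2.1.1, which covers BSI/sepsis as well as HAP/VAP and cIAI, asks for absence of the baseline pathogen from an appropriate specimen. If a culture cannot be obtained and "the subject has a successful clinical outcome, the response will be presumed to be eradication". SAP section 8 repeats this. The Synopsis (Efficacy Assessments), Protocol 3.1 and the microbiology footnote of Appendix 1 also allow presumed eradication. They tie it to resolution of all presenting signs and symptoms, which they label clinical cure.

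**Indeterminate.** Protocol 7.6.2.1.1 also has a category for "No culture obtained from an appropriate clinical specimen or additional antibiotic therapy for the treatment of the current infection including missed sampling". It does not say whether this or the presumption takes precedence. SAP section 8 narrows the category: sampling missed because the subject had done well clinically no longer falls in it.

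**Per-subject rule.** SAP section 8 adds: "For subjects with baseline infection other than cUTI who achieved clinical cure at corresponding visit, the response will be considered as Eradicated". The sentence is not limited to subjects without a culture.

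**Sampling.** Protocol 3.1 states: "The time points for collection of microbiological specimens are otherwise not prespecified by the protocol". Protocol 7.5.3.2 states: "After initiation of study treatment in the multiple-dose phase, clinical specimens should be obtained where possible, if clinically indicated" and "Blood cultures should be collected if clinically indicated and sent to the local laboratory".

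**The concern.** Clearance of the bloodstream is the one objective component of BSI/sepsis cure. When there is no follow-up blood culture, the plan sends the reader from cure to eradication and back to cure, and no observation decides either. This situation is foreseeable: follow-up cultures are unscheduled and depend on clinical indication, and the EOS visit may be a phone call.

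Clinical and microbiological response are both named in the secondary objective (cefiderocol alone) and again in the exploratory objectives. SAP 8.1.1 and 8.1.2 tabulate both by baseline pathogen and MIC. A reader of the report would naturally take agreement between the two as corroboration. For unsampled bacteraemic subjects that agreement would come from the definitions, not from data.

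**Working it through.** The plan states no figure on this point, so there is none to reproduce. The check asks which pairs of outcomes are consistent with the definitions.

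**Notation for one bacteraemic subject.** S = 1 if signs and symptoms have resolved or substantially improved. C = 1 if clinical cure. E = 1 if eradication.

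- Cure (Protocol 7.6.1.1.3, SAP section 8): C = 1 only if S = 1 and E = 1.
- Eradication when a culture exists (Protocol 7.6.2.1.1): E = 1 if negative, E = 0 if positive.
- Eradication when no culture exists: depends on the rule chosen, as below.

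**Subject with S = 1 and no follow-up culture**

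| Rule for the missing culture | Source | Consistent (C, E) |
|---|---|---|
| E follows the clinical outcome (E = C) | Protocol 7.6.2.1.1; SAP section 8 | (1, 1) and (0, 0) |
| E follows signs and symptoms only (E = S) | One reading of Synopsis, Protocol 3.1, Appendix 1 | (1, 1) only |
| Clinical cure counts as eradicated; otherwise not shown | SAP section 8, per-subject sentence | (1, 1) and (0, 0) |
| No culture means eradication not shown | Protocol Indeterminate category, if it takes precedence | (0, 0) only |

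Under the first and third rules both answers satisfy the text, so the text does not choose. Under the second rule the bacteraemia condition adds nothing to S. Only the fourth rule settles the case without presuming clearance, and nothing gives it precedence.

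**Subject with S = 1 and a culture.** Under the cure and eradication definitions a negative culture gives only (1, 1) and a positive culture gives only (0, 0), so there is no loop. Under the SAP per-subject sentence taken alone, a positive culture leaves both (1, 1) and (0, 0) consistent, because that sentence does not refer to the culture result.

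**Which way scoring leans.** A child whose signs have resolved meets none of the clinical failure criteria in Protocol 7.6.1.1.3, and clinical Indeterminate is reserved for loss to follow-up. Cure is therefore the nearest clinical category. Once cure is entered, the SAP sentence supplies eradication, and SAP 6.4.2, which counts missing or indeterminate outcomes as nonresponse, no longer applies.

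**Size, as illustration only.** The documents give neither the number of bacteraemic subjects nor the share without a follow-up culture.

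- One subject in a multiple-dose ITT cohort at the minimum of 10: 1/10 = 10 points.
- One subject in the minimum multiple-dose total of 3 × 10 = 30: 1/30 = 3.3 points.
- In a MITT or cefiderocol-alone subset of m subjects: 100/m points, which is larger when m is below 10 (cohort) or 30 (total).
- Assume 10 bacteraemic subjects, all improved, with every culture taken negative. Cure is 10/10 under presumption. If a documented negative is required and 20%, 50% or 80% have no culture, it is 10 × 0.8 = 8/10, 10 × 0.5 = 5/10 or 10 × 0.2 = 2/10.

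**The case against.** The strongest reply is that the protocol already has a place for this child. Presumption applies only when a culture cannot be obtained. A child not re-bled because there was no clinical indication is arguably a case of missed sampling, hence Indeterminate and a nonresponder under SAP 6.4.2. This stands to the extent that the defect is partly one of precedence. It does not remove the problem, because no precedence is stated and the SAP takes sampling missed through clinical success out of Indeterminate.

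Second, Protocol 7.6.2.1 bases the per-subject outcome on specimens obtained at any time after treatment starts, so an on-treatment negative blood culture can already serve later visits. This stands. The loop concerns subjects with no follow-up blood culture at all, not everyone left unsampled at Posttreatment or EOS.

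Third, the Synopsis, Protocol 3.1 and Appendix 1 ask for resolution of all presenting signs, which is stricter than substantial improvement. That is so, but the same sentences equate it with clinical cure, which leads back to the cure definition.

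Fourth, efficacy is descriptive, is outside the sample size rationale (Protocol 9.2), and is described in Protocol 7.7 as deliberately not rigorous. This limits the weight of the point. It does not justify reporting two outcomes as separate findings when one was inferred from the other.

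A reader might also infer that the SAP per-subject sentence overrides a positive culture. The SAP does not establish that: its Persistence entry stands alongside, and the order between them is simply not given.

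**Conclusion.** The point holds for multiple-dose BSI/sepsis subjects with bacteraemia and no follow-up blood culture. For them the definitions determine neither outcome, and the SAP wording leans towards scoring both as success without microbiological evidence.

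Three stronger readings are not supported:

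- **That the plan necessarily inflates BSI cure and eradication.** The text is equally consistent with assigning neither; the lean comes from the SAP wording and the lack of a fitting clinical category.
- **That the effect is 10 to 30 points on each endpoint.** This needs one to three such subjects per cohort, which is an assumption. It also uses ITT denominators, whereas microbiological outcomes are analysed in the MITT population. The size is unknown.
- **That the two efficacy endpoints are one and the same throughout.** The cUTI outcome definitions contain no presumption. In HAP/VAP and cIAI the inference runs one way only, since cure there does not require eradication. Sampled bacteraemic subjects are settled by their culture under the cure and eradication definitions.

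The primary safety and PK objectives are untouched. The change should still be made, because a stated rule lets two secondary endpoints certify each other and the repair is cheap.

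**What to change.** Amend Protocol 7.6.1.1.3 and 7.6.2.1.1, the matching presumption text in the Synopsis, Protocol 3.1 and Appendix 1, and SAP section 8 including its per-subject sentence. Changing 7.6.2.1.1 alone would leave the other routes open.

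1. Exempt bacteraemia from presumed eradication, and state that any culture result overrides clinical cure.
2. For analysis, define documented clearance as at least one negative blood culture after the first cefiderocol dose with no later positive for the baseline pathogen. Use cultures already recorded at any time.
3. If there is no such culture result, score the microbiological outcome Indeterminate.
4. Keep documented clearance as the condition for confirmed clinical cure. Show improved subjects without a culture on a separate line, for example *symptoms resolved or improved, clearance not documented*, and do not count them in confirmed cure.
5. For the other non-cUTI infections, report documented and presumed eradication separately.

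**Cost.** Wording in both documents and one programmed flag. No new samples are needed, because Protocol 7.5.3.2 already has multiple-dose local culture results entered in the eCRF. The downside is somewhat lower confirmed BSI cure and eradication rates.

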7.5.4 Adverse Events Assessments

7.5.4.1 Definition and Assessment of Adverse Events

An AE is defined as any untoward medical occurrence in a subject administered a pharmaceutical product (including investigational drug) during the clinical investigation. An AE can therefore be any unfavorable and unintended sign (including an abnormal laboratory finding), symptom, or disease temporally associated with the use of an investigational product, whether or not considered related to the investigational product. If signs and/or symptoms are part of a diagnosis, the diagnosis should be reported as the AE rather than the individual signs and/or symptoms.

Adverse events will be found by the subject's or subject's parent(s)/LAR spontaneous complaint, subject comment cards, or as a result of nonleading questions, physical examination, vital signs, or laboratory tests. Adverse events include any occurrences that are new in onset or aggravated in severity or frequency from the baseline condition, or abnormal results of diagnostic procedures, including laboratory test abnormalities. Concurrent medical conditions present at baseline that worsen will be considered as AEs. The progression of the study qualifying infection (poor or no response, aggravation, or relapse of current infection) is not an AE (unless the outcome is serious) in the study. This statement applies until the Posttreatment visit. Any aggravation or relapse of the study qualifying infection after the Posttreatment visit should be considered an AE.

New onset infection involving another site such as BSI is considered an AE.

Hospitalizations for preplanned or elective procedures to treat a preexisting condition that did not worsen after study start will not be considered AEs or SAEs. The exception is when the subject experiences another event or has an outcome that is fatal, life-threatening, leads to prolonged hospitalization, or is considered to be clinically significant during/following the procedure.

The investigator or subinvestigator is responsible for assessing AEs. Adverse events should be fully investigated and recorded in detail including onset date, end date, date of outcome assessment (if outcome is other than not recovered, recovering, or unknown), severity, seriousness with a category of seriousness, causal relationship with the study treatment, action taken to manage the AE, and outcome of the AE in the eCRF.

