7.6.1.1.1 HAP/VAP/cIAI

- **Clinical Cure:** Resolution or substantial improvement of baseline signs and symptoms of pneumonia/cIAI.
- **Clinical Failure:** No apparent response to therapy; persistence or worsening of baseline signs and/or symptoms of pneumonia/cIAI; reappearance of signs and/or symptoms of pneumonia/cIAI; development of new signs and/or symptoms of pneumonia/cIAI requiring antibiotic therapy other than, or in addition to, study treatment therapy; progression of chest radiographic abnormalities; or death due to pneumonia/cIAI.
- **Indeterminate:** Lost to follow-up such that a determination of clinical cure/failure cannot be made.

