7.6.2.1 Microbiological Outcomes

An overall per-subject microbiological outcome for the specimens collected and obtained at any time after initiation of study treatment will be determined based on the individual microbiological outcomes for each baseline Gram-negative pathogen. The microbiological outcomes determined by investigator will also be entered in the eCRF. Emergent (ie, nonbaseline) pathogens are considered separately, and do not affect the per-subject microbiological outcome.

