6.2. Key Definitions

6.2.1. Baseline Definition

Baseline for weight, height: Baseline is the last available data within 4 days prior to Treatment Day 1 or on Treatment Day 1.

Baseline for other vital sign parameter: Baseline is the last available data prior to Treatment Day 1 pre dosing.

Baseline for Laboratory Evaluations: Baseline is the last available data within 4 days prior to Treatment Day 1 or on Treatment Day 1 for single dose phase, and are within 4 days prior to Treatment Day 1 or at Screening visit (excluding before 4 days prior to Treatment Day 1) in multiple dose phase.

Baseline for Gram-Negative Pathogen: Baseline pathogens will be determined from appropriate specimens from the baseline infection site collected within the 4 days prior to the first dose of cefiderocol in the multiple-dose phase of this study. If specimens are collected on multiple dates before the first infusion, the specimens collected on the latest date for each pathogen will be used to determine baseline pathogens. If there are more than one appropriate clinical specimens on the latest date, appropriate clinical specimens for the baseline will be selected following below priority.

This document is confidential.

1. When pathogens are identified as resent samples for the same subject, the larger req num ending with S02 will be used for analysis
2. When multiple records identified from same pathogen, same date, pathogen with the highest quantitative value will be considered
3. When multiple records identified from same pathogen, same date, pathogen with any valid minimum inhibitory concentration (MIC) for cefiderocol will be considered.

In case different Gram-negative pathogens are obtained from specimens from the baseline infection site, all of them will be considered as baseline pathogens.

Baseline for Microbiology Susceptibility: Microbiology Susceptibility tested for pathogens identified from IHMA. Baseline followed the baseline Gram-Negative Pathogen.

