6.2.3. Appropriate clinical specimens

Appropriate clinical specimens are defined as sputum, tracheal aspirate, bronchoalveolar lavage (BAL) fluid, protected specimen brush, pleural fluid, lung biopsy for HAP/VAP, blood for BSI/sepsis/cIAI, or urine for cUTI. Specimens that were collected from other sites may be considered as appropriate specimen. This will be determined by the medical monitor. If the infection site is "other", it will be determined whether the specimen is an appropriate clinical specimen or not by medical monitor. The time window of the 4 days prior to the first dose of cefiderocol will be determined based on time unit, ie within 5760 min from the first infusion.

Eligibility of subjects into the MITT Analysis Population will be based on local lab results of baseline pathogens if the microbiological culture results are not sent to a central lab for confirmation or if central lab results are missing. In addition, in such a case, the local lab result will be used for analysis.

6.2.4. Day 1

Day 1 will be defined as the day of the first dose of cefiderocol.

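### Clearance of bacteraemia is a condition of cure only under the BSI/sepsis label, so a HAP/VAP or cIAI child whose blood still grows the baseline pathogen can be scored Cure and Eradicated; the cUTI gap is narrower

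*Protocol*

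**What the plan says.** Outcome is scored in the multiple-dose phase by infection type.

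**Clinical Cure**
- BSI/sepsis (protocol 7.6.1.1.3, repeated in SAP 8): improvement in signs and symptoms, plus "Subjects with bacteremia must have eradication of bacteremia caused by the Gram-negative pathogen".
- HAP/VAP/cIAI (7.6.1.1.1): "Resolution or substantial improvement of baseline signs and symptoms of pneumonia/cIAI". Nothing further is required.
- cUTI (7.6.1.1.2): "Resolution or substantial improvement of baseline signs and symptoms of cUTI, or return to preinfection baseline if known", and the sentence then adds "such that no antibiotic therapy is required for the treatment of the current infection".

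**Microbiological outcome**
- cUTI eradication and persistence are both read from a urine culture (protocol 7.6.2.1.2, SAP 8). Additional antibiotic for the current infection gives Indeterminate, and SAP 6.4.2 counts Indeterminate as nonresponse.
- For the other types, the outcome is read from an appropriate clinical specimen. SAP 6.2.3 lists respiratory and lung material, ending with "lung biopsy for HAP/VAP, blood for BSI/sepsis/cIAI, or urine for cUTI". It then lets the medical monitor accept specimens from other sites.
- "Baseline pathogens will be determined from appropriate specimens from the baseline infection site" (SAP 6.2.1).
- For the per-subject result, SAP 8 says that a child with any infection other than cUTI who is clinically cured at a visit is considered eradicated at that visit. The same list says that persistence of any baseline Gram-negative pathogen is entered as Persistence. No order between the two is given.

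Protocol 4.3 has the infection type recorded in the eCRF. Neither document says how to label a child who has a local infection and is also bacteraemic.

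**The concern.** The bacteraemia condition follows the infection label, not the blood culture. Two children with the same organism persisting in blood can get different clinical outcomes because one was recorded as BSI and the other as pneumonia or cIAI. The label and the clinical response are both investigator-recorded in an open-label study.

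Persistence of the qualifying organism in blood is strong evidence against microbiological success. For HAP/VAP and cIAI the plan can record it as success on both endpoints: cure is judged on signs and symptoms, and that cure then supplies the eradication. The cefiderocol-alone results for clinical and microbiological response form the secondary objective. The combination and all-treated results are exploratory. All are reported in small groups.

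**Working it through.** The plan states no figure that depends on this rule, so there is nothing to reproduce. The check is to pass one case through each set of definitions: at the visit being scored, signs and symptoms of the labelled infection have improved, but a blood culture grows the baseline Gram-negative pathogen.

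| Label | Clinical Cure | Microbiological outcome |
|---|---|---|
| BSI/sepsis | Blocked by the bacteraemia sentence | Blood is a listed specimen: Persistence |
| cIAI | Allowed; no blood condition | Blood is a listed specimen, so the per-pathogen result is Persistence; the per-subject cure rule in SAP 8 gives Eradicated |
| HAP/VAP | Allowed; no blood condition | Blood is not listed but may be accepted by the medical monitor; even if it is, the per-subject cure rule gives Eradicated |
| cUTI | Not blocked by the blood culture itself; blocked if antibiotic is still required for the current infection | Urine only: Eradication if urine falls below 10^3 CFU/mL; Indeterminate if additional antibiotic is given for the current infection |

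**cIAI.** The per-pathogen and per-subject tables can disagree for the same child at the same visit, because both per-subject rules in SAP 8 are met and neither is ranked first.

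**HAP/VAP.** Both endpoints can register success. Accepting the blood culture as an appropriate specimen does not settle the matter, because the cure-based rule has no exception for a positive culture.

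**cUTI.** Double success requires clear urine, improved symptoms, and either no antibiotic judged necessary for the current infection or a blood result that did not inform the assessment.

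**Scale.** Protocol 3.1 gives a minimum of 10 children per multiple-dose cohort and 30 in total. The shift from one mis-scored child in a group of n is 100/n points.
- One cohort: 100/10 = 10 points.
- All cohorts: 100/30 = 3.3 points.
- Cefiderocol-alone subset: the documents give no size. If it were 3 to 8 children (assumption), the shift is 100/8 = 12.5 to 100/3 = 33.3 points.

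**Exposure.** The documents give no bacteraemia rate. If 5% to 20% of children with a non-BSI label were bacteraemic (assumption), then even with all 30 so labelled, 0.05 × 30 = 1.5 to 0.20 × 30 = 6 children would come under the rule. Only those with a positive follow-up blood culture and otherwise good signs would be mis-scored.

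**The case against.** The strongest case against has five parts.

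1. **cUTI has backstops.** A child who needs antibiotic for a persisting organism does not meet the cUTI cure definition, and additional antibiotic makes the microbiology Indeterminate, hence nonresponse. This stands, and it is why the cUTI gap is the smaller one. HAP/VAP and cIAI cure has no equivalent clause.

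2. **Blood can be scored outside BSI.** A reader might infer that blood can never count for HAP/VAP or cUTI. For HAP/VAP the documents do not support that, because SAP 6.2.3 leaves room for other specimens. Only the cUTI microbiological definitions confine scoring to one specimen. The discretion does not remove the HAP/VAP problem, for the reason shown in the table.

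3. **Two other clauses prove less than they seem to.** "Emergent (ie, nonbaseline) pathogens are considered separately, and do not affect the per-subject microbiological outcome" concerns organisms that were not present at baseline, so it does not exclude a baseline pathogen found in blood. "New onset infection involving another site such as BSI is considered an AE" classifies an event for safety; it does not say the event cannot also be a clinical failure. Neither should be used to argue that the plan rules out failure.

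4. **The case is self-limiting.** Protocol 7.5.3.2 has blood cultures taken only when clinically indicated, and a child cultured after treatment will often have signs that already count against cure. The investigator also weighs objective data through an open list of examples (7.6.1). This lowers the frequency but requires nothing of the investigator.

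5. **Efficacy is deliberately light here.** Protocol 7.7 says efficacy assessment is intentionally not rigorous, there is no inferential testing, and sample size ignores efficacy. That limits the consequence. It does not justify scoring one blood culture in opposite ways under different labels.

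It could also be said that the cure-based rule is meant only for children without a culture, as in the presumed-eradication wording of protocol 7.6.2.1.1. That may be the intent, but the per-subject sentence in SAP 8 contains no such restriction.

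**Conclusion.** The concern holds for HAP/VAP and cIAI and, more narrowly, for cUTI. As written, the plan permits Cure and Eradicated for a HAP/VAP or cIAI child whose blood still grows the baseline Gram-negative pathogen. This depends on the child keeping the local-infection label, which no rule prevents, and on the per-subject cure rule being applied as worded.

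The arithmetic consequence is 10 points per mis-scored child in a cohort of 10 and 3.3 points in 30, and more in smaller subsets. No sample size, error rate or decision rule changes.

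A reader might go further and infer that the reported rates are biased upward overall. That is not shown. This particular error runs only toward success, but missing and indeterminate outcomes count as nonresponse, and SAP 8.1 itself expects EOS results to be underestimated. The documents contain no rate from which a net direction could be derived. The point deserves correction because the rules are inconsistent and the repair is cheap, not because a large distortion has been demonstrated.

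**What to change.** Make three edits, using only blood cultures already captured:

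1. In protocol 7.6.1.1 and SAP 8, apply the existing bacteraemia condition to every infection type: a captured blood culture that grows a baseline Gram-negative pathogen, taken at or after EOT and attributable to the visit being scored, precludes Clinical Cure at that visit.
2. In protocol 7.6.2.1 and SAP 6.2.3 and 8, count such a culture as Persistence for HAP/VAP and cUTI as well.
3. In SAP 8, state that documented Persistence takes precedence over eradication presumed from clinical cure.

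The timing limit in the first edit matters. A broader rule, blocking cure after any positive blood culture without a later negative one, would deny cure to a child who was positive early in treatment, recovered and was never recultured, and the protocol does not require a repeat culture. Early on-treatment positives without a repeat, and children with no follow-up blood culture, should be scored as they are now.

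If limiting the condition to BSI/sepsis is deliberate, the documents should say so and state how concurrent bacteraemia is labelled.

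The cost is a few sentences and a small derivation. Multiple-dose culture results already go into the eCRF (protocol 7.5.3.2), and protocol 9.1 allows minor SAP changes to be finalised before database lock. No new sampling is needed. The downside is slightly less favourable cure and eradication rates.
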